- g. Active use of the System will be observed by a Technical Observer, i.e., an IRB-approved member of the investigative team. The Observer will generally observe the system continuously, with a minimum of at least one observation every 15 minutes. These observations provide additional assurance that there is no potential interference with any other aspect of the patient's care; that the technical performance of the System is grossly consistent with its intended operation; to ensure that the patient doesn't express any concern; and to ensure that the nurse doesn't express any concern. By protocol, if the nurse, patient, or patient family member states any negative perception of the investigational system, the Technical Observer will ask whether the nurse/patient/family member prefers the protocol to stop, and will oblige if this is requested. If the protocol is stopped early by request of the nurse, patient, or family member, the Technical Observer will ask for feedback after stopping the protocol and removing the apparatus: "You requested that we stop our testing protocol. Can you tell us why, to help us ensure that this testing protocol is safe and appropriate for other ICU patients?" The protocol will also terminate early if an Exclusion criterion is met: receiving two simultaneous vasopressors running at maximum doses (per the ICUs own protocols) or who is on one maximum-dose vasopressor and has a contraindication to receiving a second vasopressor (e.g., insufficient vascular access). During the protocol, the nurse will have the option to adjust the Index Threshold per their clinical practice preferences, and the Technical Observer will provide technical support of the nurse decides to do this. Lower thresholds for the Index Threshold provide higher sensitivity and earlier warnings at the expense of reduced positive predictive value. Higher thresholds the Index Threshold provide lower sensitivity and less advanced notifications at the benefit of

higher positive predictive value. Within the second hour of the protocol session, the Technical Observer will explicitly confer with the nurse about the operation of the system, confirming whether the nurse understands the visual display elements, whether the nurse would like to adjust the Index Threshold, and whether the nurse has any concerns about the investigational display or the protocol. This check-in will occur at a time when the nurse is not occupied with direct patient care.

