- l. All ICU clinicians, including physicians, RN, NPs, and PAs, will be educated about the study by email. The "investigational protocol information" document will be sent to all clinicians in the department at least every 6 months. Before any new enrollments, we will confer with the ICU director whether there are new clinicians working since the last enrollment who need to be emailed (i.e., new staff or residents starting their ICU clinical rotation).

Data to be collected and when the data is to be collected

Subjects will be enrolled during periods when the study staff are available to conduct the protocol for a minimum of four hours of data collection (plus an extra hour for apparatus cleaning as well as conducting the post-enrollment clinician survey). The maximum duration of data collection for a given subject will be eight hours, i.e., the duration of a shift for the study staff.

During data collection, the System will automatically archive the subject's vital signs through time. The system will also auto-log any abnormal functionality.

The technical observer will annotate any clinical interventions; any technical abnormality observed in System operation; and any concerns by the clinical staff or the patient or the patient's family. The technical observer will also provide subjective descriptions of the patient's apparent state (for purposes of better understanding retrospective data analysis after the study is complete).

In the final hour of each data collection session, we will ask the nurse to complete a brief questionnaire that provides specific feedback and also indicates whether performance of the investigational system was generally acceptable (see below). This will conclude data collection.

“Thank you for participating in the clinical testing of our decision-support system. We would like your final feedback about the following topics.”

- Question 1: Do you agree or disagree with the following statement:

“This system will make it generally easier to keep blood pressure within the goal range during continuous vasopressor infusion?”

 - 1- Strongly disagree
 - 2- Disagree
 - 3- Neutral
 - 4- Agree
 - 5- Strongly agree
- Question 2: What feature(s) of the system do you think will be most useful, either to yourself or to other typical ICU caregivers?
- Question 3A: Did you identify any display output by the system that is confusing, or inaccurate?
- Question 3B (if answer “yes” to 3A): If so, what?

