4. Ensure that the data reported in REDCap from each nursing-subject interview are complete.
5. Ensure that the log files for each patient-subject session do not include any error- or critical-level message (except for those that are expected to naturally occur during system shut-down, which would be after each patient-subject data collection session has been completed).
6. Ensure that any event note for the patient's ICU documentation record that involved more than the primary nurse as a clinical responder was captured by the Technical Observer's annotations.

Safety monitoring

After the first 5 subjects are enrolled, the nurse-subject responses to the questionnaire will be submitted to the IRB, along with a report of any adverse events.

The following events represent possible adverse events:

- (a) the Technical Observer (a member of the research team) identifies any failure of the software and terminates the session (the Technical Observer may also terminate for any subject reason related to any subjective perceived negative impact on the subject's care);
- (b) if the nurse indicated that the protocol was having any negative effect on the patient's care, either during the execution of the protocol session, or in responses to the questionnaire that is conducted after every enrollment ("Question 3: Did you identify any output by the system that is dangerously confusing, or dangerously inaccurate? If so, what?"; and "Question 4: This system provides lots of visual information, which might be distracting. At any time, did the system actually distract you from noticing something important about your patient or administering important care to your patient, such that your response to the patient was delayed?");
- (c) if the patient/close family member indicated any discomfort with the protocol session.
- (d) Review of the software logs indicates any error-level or critical-level log statements were generated.

(e) Review of the software data archive indicates any interruption in the routine monitoring of vital-signs.

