If any of these events occur, within 5 days, we will assess whether the event increased the patient-subject's risk of a serious adverse event. This assessment will include conferring with the study PI; the Blake 12 intensive care unit chief; and the Blake 12 intensive care unit nursing leader, to evaluate whether the event represented an event that is more than minimal risk to future subjects. If any of these (the study PI; the Blake 12 intensive care unit chief; and the Blake 12 intensive care unit nursing leader) judges that the event poses more than minimal risk to future subjects, we will halt the study.

Outcomes monitoring

As detailed above, the independent monitor will evaluate the outcomes data, including the completeness of all data collection instruments; the accuracy of the system software archive (based on a comparison with the Technical Observer's hourly annotation of vital signs); and the presence of time-stamped software logs for each enrolled patient-subject.

Adverse event reporting guidelines

Adverse event means any untoward medical occurrence associated with the use of an intervention in humans, whether or not considered intervention-related (21 CFR 312.32 (a)).

We will rely on the system data archive; annotations by the Technical Observer; and interview responses by the nurses to reveal adverse events. Adverse events will include all sustained hypotension episodes (as per Section 3.2.2.1 of this IDE Application); tachyarrhythmias (HR > 150 bpm) or bradyarrhythmias (HR < 50 bpm) that persist for more than ten minutes; needs for chest compressions or defibrillation; or any unscheduled bedside response by the ICU care team involving more than the patient's primary nurse.

An adverse event (AE) or suspected adverse reaction is considered "serious" if, in the view of the investigator/sponsor, it results in any of the following outcomes: death, a life-threatening adverse event, inpatient hospitalization or prolongation of existing hospitalization, a persistent or significant incapacity or substantial disruption of the ability to conduct normal life functions, or a congenital anomaly/birth defect. Important medical events that may not result in death, be life-threatening, or require hospitalization may be considered serious when, based upon appropriate medical judgment, they may jeopardize the participant and may require medical or surgical intervention to prevent one of the outcomes listed in this definition.

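### P.9 trigger (b) counts harm to care reported by the nurse only, so the same concern recorded from a physician or other clinical staff member does not by itself start the 5-day review

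*Combined protocol and SAP*

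**What the plan says.** P.9, Safety monitoring, sets out five events and ties a review to them: "If any of these events occur, within 5 days, we will assess whether the event increased" the patient-subject's risk of a serious adverse event. The review involves the PI, the ICU chief and the ICU nursing leader, and the study halts if any one of them judges the risk to later subjects to be more than minimal.

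The five events are:
- (a) The Technical Observer finds a software failure and ends the session. A parenthesis adds that "the Technical Observer may also terminate for any subject reason related to any subjective perceived negative impact" on the subject's care.
- (b) Applies "if the nurse indicated that the protocol was having any negative effect" on care, either during the session or in the questionnaire.
- (c) Applies "if the patient/close family member indicated any discomfort with the protocol session".
- (d) Error-level or critical-level statements appear in the software logs.
- (e) The data archive shows an interruption in vital-sign monitoring.

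P.5, under data to be collected, gives the Observer a wider recording duty. It includes "any concerns by the clinical staff or the patient" or the patient's family. Step l of P.5 also tells the wider team about the study: "All ICU clinicians, including physicians, RN, NPs, and PAs, will be educated about the study by email".

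**The concern.** The people whose concerns are recorded and the people whose concerns trigger review are not the same. P.5 collects concerns from clinical staff, patient and family. P.9 acts on concerns from the nurse, patient and family. Followed literally, a relative's expression of any discomfort must go to three reviewers who can halt the study. A treating physician's recorded statement that the protocol is affecting care need not.

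What is at stake is the completeness of a safety rule. The nurse is the user of the display, and Question 4A asks that same nurse whether the system distracted them from something important. A nurse who was distracted may not be the person best placed to notice it. Another clinician at the bedside is a natural second source.

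**Working it through.** No formula applies and the plan states no figure to reproduce. The check sets the provisions side by side and follows one case through them.

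**Step 1. What each trigger rests on (P.9, Safety monitoring).**

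| Trigger | Rests on |
|---|---|
| (a) | The Observer's own finding and termination |
| (b) | What the nurse indicates |
| (c) | What the patient or close family member indicates |
| (d) | Review of software logs |
| (e) | Review of the data archive |

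Two of the five, (b) and (c), rest on what someone outside the research team says. One rests on the Observer and two on data review (2 + 1 + 2 = 5).

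**Step 2. A test case.** During a session a physician says that the protocol is interfering with the patient's care. The Observer annotates this, as P.5 requires. The session continues, the nurse does not repeat the point, and nothing abnormal appears in the logs or archive.

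- (a) is not met. There is no software failure and no termination. The parenthesis lets the Observer terminate but does not require it. The text also leaves unclear whether a termination without software failure is itself a listed event.
- (b) is not met, because the speaker is not the nurse.
- (c) is not met, because the speaker is neither patient nor family.
- (d) and (e) are not met, by construction of the case.

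So the recorded concern does not start the 5-day review.

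**Step 3. What else could pick the case up.**

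- *Adverse event detection.* P.9, Adverse event reporting guidelines, names three sources for finding adverse events: the system archive, the Observer's annotations and the nurse interviews. The physician's recorded concern is thus within a named source. Any adverse event it reveals is recorded and assessed for causality by the investigator. The listed adverse events, however, are occurrences such as sustained hypotension or an unplanned bedside attendance by staff beyond the primary nurse. A stated concern without such an occurrence is not among them, and that section does not bring in the ICU chief or nursing leader.
- *PI access.* P.9 makes the PI reachable throughout every session and has the PI run at least the first one. Nothing prevents voluntary escalation.
- *Observer checks.* Step g of P.5 says that the observations give "additional assurance that there is no potential interference with any other aspect" of the patient's care. That purpose holds whoever raises the problem, but no escalation step is attached to it.
- *Report to the IRB after the first 5 subjects.* This covers the nurse questionnaires and adverse events. It does not list Observer annotations of staff concerns.

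**Result.** The gap is confined to a concern about harm to care that a clinician other than the nurse voices, that the nurse does not repeat during the session or in the questionnaire, that the Observer does not act on by terminating, and that no adverse event, log error or archive interruption accompanies.

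**The case against.** The strongest reply is that the remaining case is very small and that the choice of named reporters fits the design. The nurse and the patient are the study's subjects, and the nurse is the user. The nurse has several chances to repeat a colleague's concern: during the session, at the second-hour check-in and in the questionnaire. Other clinical providers also have a say at enrolment, since their discretion is an exclusion criterion. All of this stands, and it is why the point is minor. It does not change the literal result in the test case, and the enrolment criterion is not written as an in-session stop.

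A reader might infer that clinicians' concerns are collected and then go nowhere. The documents do not support that, because Observer annotations are one of the named sources for revealing adverse events.

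A reader might also infer that the stop offer in step g, which applies "if the nurse, patient, or patient family member states any negative perception of the investigational system", should be widened in the same way. That does not follow. The rest of that passage asks only the nurse, patient or family whether to stop, so adding staff to the condition alone would be incoherent. Its threshold is also any negative perception of the system, which is much broader than harm to care. A usability remark from a passing clinician could then prompt a stop offer in a session planned for at least four hours.

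Finally, counting which staff types the triggers name would not measure risk, so no weight is placed on such a count.

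**Conclusion.** The point holds in limited form. As written, a recorded statement by a physician, NP, PA or other staff member that the protocol is harming care does not by itself start the 5-day review. This is a stated trigger rule that is slightly too narrow for the information the protocol already collects.

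The size is minor. The documents give no rate for such concerns and none is assumed. No endpoint, analysis or sample size is touched.

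The conclusion rests on two readings. The first is that the nurse in (b) means the patient's nurse who uses the system, not clinical staff at large. The second is that the 5-day review attaches only to events (a) to (e). It is also subject to one unknown: P.7 refers to Section 4 of the IDE Application for detailed risk assessment, and that section is not in the documents. If it already escalates staff concerns, what is missing from P.9 is only a cross-reference.

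**What to change.** In P.9 trigger (b), after the reference to the nurse, insert: or any other member of the clinical staff. Leave the rest of (b), including the questionnaire route, as it is. If Section 4 of the IDE Application already covers concerns from other staff, cite it in P.9 instead.

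This is a cheap improvement of one phrase. It uses the Observer annotations already required by P.5 and the three reviewers already named in P.9. The downside is possibly a few more events to assess over the 20 sessions.

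### The 5-day review that can halt the study has no explicit link to serious clinical events: death, chest compressions or defibrillation in a session does not automatically trigger it

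*Combined protocol and SAP*

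**What the plan says.** Section P.9 treats adverse events under two headings.

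Under Safety monitoring, a list introduced by "The following events represent possible adverse events" has five items:

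- (a) the Technical Observer "identifies any failure of the software and terminates the session", with a parenthesis that the observer "may also terminate for any subject reason related to any subjective perceived negative impact on the subject's care";
- (b) a report from the nurse of any negative effect on care, whether said during the session or given in the answers to Questions 3 and 4;
- (c) discomfort with the session voiced by the patient or close family;
- (d) "Review of the software logs indicates any error-level or critical-level log statements were generated";
- (e) a gap in vital-sign monitoring found in the data archive.

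The next paragraph starts the review: "If any of these events occur, within 5 days, we will assess whether the event increased" the patient's risk of a serious adverse event. The PI, the ICU chief and the ICU nursing leader are consulted. If any one of them finds that the event exceeds minimal risk for later subjects, the study is halted.

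Under Adverse event reporting guidelines, the clinical events are defined: sustained hypotension, fast or slow heart rhythms lasting more than ten minutes, "needs for chest compressions or defibrillation; or any unscheduled bedside response by the ICU care team" beyond the primary nurse. The same subsection defines when an event is serious, and death comes first among the outcomes. All adverse events are recorded, and the investigator grades each for relationship to the intervention.

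**The concern.** The procedure that can stop the study is attached to the first list only. Followed as written, a single error-level log line requires a three-role review within 5 days. A patient who needs chest compressions during a session with no software error, complaint or monitoring gap does not require one.

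This matters because of what the device does. It forecasts blood pressure and alerts the nurse, so output that misleads need not leave an error in the log or prompt a complaint. A serious clinical event is one of the ways such a fault could come to light. As the text stands, the step assigned for that event is causality grading by the investigator, and no action follows from any grade. P.1 discloses that investigators invented the software and may benefit financially. It also states that the institution found no significant risk to participants or to research integrity. A review that brings in two people named by their unit role is therefore a useful safeguard, and serious clinical events are where it would be most wanted.

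**Working it through.** No formula applies. The check is a comparison of texts.

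**Step 1: what the review refers to.** The trigger sentence directly follows items (a) to (e). The lead-in to that list contains no wording that would make the items mere examples. The review also asks whether the event raised the risk of a serious adverse event. A serious event is thus treated as a possible consequence of a trigger, not as a trigger.

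**Step 2: clinical events against triggers.**

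| Clinical event in P.9 | Named in (a) to (e)? | Called expected in P.9? |
|---|---|---|
| Sustained hypotension | No | Yes |
| Sustained tachyarrhythmia or bradyarrhythmia | No | Tachyarrhythmia only |
| Chest compressions or defibrillation | No | No |
| Unplanned attendance beyond the primary nurse | No | Yes |
| Death or another serious outcome | No | No |

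The count is 0 of 4 clinical classes, and 0 of the serious outcomes, among 5 triggers.

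**Step 3: indirect routes into the review.** A serious clinical event can arrive through:

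- (b), if the nurse reports a negative effect on care or answers Question 3 or 4 accordingly;
- (c), if the patient or family voices discomfort;
- (e), if the archive shows an interruption;
- (a), on one reading: its main clause needs a software failure and a terminated session, but the parenthesis may be meant to make termination for perceived harm to care a trigger as well. The text does not settle this.

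Each route needs a further circumstance besides the clinical event.

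**Step 4: other handling of clinical events.**

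| Provision | Leads to |
|---|---|
| Causality grading of every adverse event (P.9) | A grade, with no action attached |
| Serious, unexpected and related events (P.9, Independent monitoring, FDA items) | FDA report within 7 calendar days |
| Unanticipated adverse device effects (end of P.9) | IRB form within 5 working or 7 calendar days; sponsor evaluation reported within 10 working days |
| Report after the first 5 of 20 subjects (P.9, Safety monitoring) | One submission to the IRB |
| Independent monitor (P.9) | Checks of completeness, archive accuracy, logs and capture of multi-clinician event notes |
| Early stopping in P.5, items g and j | Ends one session, not the study |

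None of these refers to the 5-day review or to a decision to halt the study.

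**The case against.** The best defence is that the two lists do different jobs. The first screens for device and process hazards, and the second covers clinical adverse events, which have their own recording, grading and reporting. P.9 calls hypotension, multi-clinician responses and tachyarrhythmias expected in these patients, which is a sound reason not to make each one a trigger. The plan also looks for the feared mechanism in every session. The questionnaire asks about confusing or inaccurate output, possible management error, and distraction that delayed a response, and answers to Questions 3 and 4 feed trigger (b).

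Much of this stands. It rules out three stronger readings that a reader might infer:

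- *A death or arrest can never reach the review.* It can, by the routes in Step 3.
- *Serious clinical events are ignored.* They are recorded, graded and, where they qualify, reported.
- *No other rule could halt the study for a clinical event.* That can be said only of the supplied text. The protocol is an appendix to an IDE application and refers to its Sections 3.2.2.1 and 4, which were not supplied.

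The defence does not close the gap. The questionnaire route depends on the nurse connecting the event with the system. The statement on expected events does not mention death, chest compressions, defibrillation or bradyarrhythmia. The reporting routes end in a report or an evaluation, not in the three-role decision.

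**Conclusion.** The point holds as a missing link. In the supplied text, a serious clinical event during a session does not by itself start the review that can halt the study, while one error-level log line does. The extent is 0 of 4 clinical adverse-event classes, and none of the serious outcomes, among the 5 triggers. The part that matters most is narrower: events that meet the protocol's own definition of serious, and clinical events the investigator considers related. Leaving out expected, non-serious, unrelated events is defensible.

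The conclusion assumes that items (a) to (e) are a complete list, as their wording indicates, and that no rule in the unsupplied IDE sections makes the link. It does not depend on how the parenthesis in (a) is read, because that route also needs the observer to judge that care was harmed. The change is worth making: it bears on subject safety and uses roles and data already in the protocol.

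**What to change.** Reconcile the Safety monitoring list with the Adverse event reporting guidelines in P.9. State that two kinds of session event enter the existing three-role review within 5 days: events that meet the protocol's own definition of serious, and clinical adverse events that the investigator grades as related. Say which of the five causality grades count as related. If an IDE section already does this, a cross-reference is enough. Also state whether a termination under the parenthesis in (a) is a trigger.

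Keep the two lists distinct. Merging them into one definition would turn every expected episode of hypotension into a trigger.

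The review's first question, whether the event raised the risk of a serious adverse event, does not fit when the event is itself serious. The second question, about risk to later subjects, does fit and can be used alone in that case.

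The change takes a sentence or two and needs no new roles or data. The downside is some additional reviews. The serious definition includes a clause on important medical events that rests on judgement, and these are vasopressor-dependent patients, so the number need not be small. The documents give no event rate, so it cannot be stated. The change concerns who reviews an event, not how any patient is managed.
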